Appendix A – Study Recruitment Flyer

Appendix B – Phone Call Scripts

Appendix C – Eligibility Screener

Appendix D – Study Consent and Baseline Survey

Appendix E – HMHL SOP Screening & Consent Information

Appendix F – Follow-up Survey

Appendix G – Semi-structured Interview Guide

Appendix H – HMHL Data Safety Monitoring Plan

Rational and Background Information

Older Asian American adults (> 65) are a rapidly growing racial/ethnic group in the United States, in which their total population is expected to nearly double from 2016 to 2030. In the context of the COVID-19 pandemic, older adults are a particularly vulnerable group as this group has an increased risk of poor prognosis due to high rates of chronic disease such as diabetes, cardiovascular disease, and cancer. In the absence of a vaccine for COVID-19, public health strategies consisted of isolation, quarantine, social distancing, and community containment. While the preventive strategies lower the risks for exposure, these strategies pose challenges for older adults who already experience isolation due to diminishing social network. For older AA & NHPI adults, these experiences are further magnified due to language barriers to accessing information and limited ability to network with culturally relevant groups. Furthermore, a survey on life satisfaction indicated that Asian American older adults reported lower satisfaction and higher unmet social and emotional needs than other race and ethnicities.¹ Finally, increased racism since the pandemic poses another layer of complexity for Asian American older adults.

Public health efforts have repeatedly marginalized older Asians' mental health needs through systematic exclusion of non-English/Spanish speakers in national surveys. Limited English proficiency (LEP) is a term used to describe individuals who do not speak English as their primary language and who have limited ability to read, speak, write, or understand English.² According to the 2010 Census, more than 18% of the U.S. population (47 million Americans) do not speak English as their primary language, and more than 25 million speak English less than "very well."² Asian immigrants are the second largest group with LEP status after Hispanics.³ Approximately 89% of older Asian Americans are foreign-born, and 62% are LEP, with 84% of Vietnamese and Koreans reporting LEP.⁴ The LEP population experiences higher burdens in health and access to care compared to their English-speaking counterparts, but surveys do not always capture these disparities.⁵⁻⁸ For example, the prevalence of depression using data from the National Health and Nutrition Examination survey (NHANES) shows lower reports of depression (3.1%) among older Asians compared to non-Hispanic Whites (7.9%), Hispanics (8.2%), and non-Hispanic Blacks (9.2%).⁹ NHANES is in English and Spanish only. When a large study (n=175,956) attempted to include survey reminders in Chinese, depressive symptoms among older Asians (11%–21%) were greater than non-Hispanic Whites (9%), non-Hispanic Blacks (16%), and similar to Hispanics (17%–23%).¹⁰ Depression rates drastically escalated to 44% when surveys (n=2,609) were administered in five Asian languages (Asian Indian, Chinese, Filipino, Korean, and Vietnamese), with 55% of Vietnamese reporting depression.¹¹ In addition, LEP status also consistently emerges as the most prominent factor for lower mental health service use and increased unmet mental health needs among older Asians.¹¹ This methodologic limitation suggests that the burden of depression among non-English/Spanish speaking older Asian adults is not represented in the national health profiles of the U.S. population, and our current knowledge may be a small glimpse of a much larger health issue.

Mindfulness-based cognitive therapy (MBCT) is a group-based intervention rooted in Eastern ideology but taught from a secular perspective.¹² MBCT combines mindfulness training and cognitive therapy to improve emotion regulation and reduce negative emotions.¹² A core feature of MBCT is the cultivation of mindfulness, defined as a nonjudgmental awareness of present-moment experiences and an accepting attitude towards oneself and the surroundings.¹³ Several meta-analyses have demonstrated MBCT reduces depression relapse.¹⁴⁻¹⁶ and active depression.^{17-19, 20} MBCT has also been embraced in Asian countries. A systematic review of MBCT intervention among Asians showed 40 studies covering diverse groups.²¹ However, the effects of the MBCT among older Asian Americans remain understudied.

We will collaborate with a community-based organization named Asian American Resource and Information Network (AARIN) to implement an MBCT intervention with older Korean adults. This is a collaborative project between AARIN and the University of Washington (UW) will recruit 40 Korean Americans ages 50⁵ and older to participate in an 8-session MBCT program delivered by staff members of AARIN.

Specific Aims

- 1) To implement the mindfulness-based cognitive therapy (MBCT) intervention.

2) To assess the acceptability and relevance of MBCT, as well as its impact on patient reported outcomes among older Korean adults, ages 50-89.

Overall Research Design

We will conduct a single arm, pre/post pilot intervention study to examine the effect of MBCT on depression among older Korean American adults. We will recruit older Korean adults (n=40) from AARIN to complete the 8-session Healthy Mind, Healthy Living intervention, along with periodic mental health assessments.

Eligibility Criteria

Inclusion criteria: To be eligible, the participants must: (1) self-identify as a Korean person, (2) be between the ages 50 and 89, (3) has mild to moderate depressive symptoms (scores between 5-14 when assessed using Patient Health Questionnaire-9 (PHQ-9), (4) has limited English proficiency (responds “less than very well” when asked “how well do you speak English?”) and fluency in Korean (e.g. able to speak at a native level), and (5) willing to give a written consent to participate in the study.

Exclusion criteria include: Individuals will not be able to participate if they have any of the following criteria: (1) major psychiatric diseases that would interfere with participants’ ability to participate in or receive the benefit from the mental health interventions (e.g., bipolar disorder, schizophrenia, recent history of psychosis or mania, severe depressive symptoms); (2) used drugs other than those required for medical reasons; (3) serious medical conditions (e.g., poorly controlled diabetes, severe congestive heart failure) that has not been stable for at least 3 months; (4) current active suicidal or self-injurious behavior, potentially necessitating immediate treatment; (5) general conditions that would impede participation in a group intervention (e.g., cognitive impairment, tendencies toward physical aggression); (6) prior history of engaging in formal mindfulness-based interventions including mindfulness-based stress reduction, MBCT, Acceptance and Commitment Therapy, and Dialectical Behavioral Therapy; and (7) significant current meditation practice, specifically more than three hours of insight/mindfulness/vipassana meditation per week.

Participant Recruitment

AARIN will recruit older Korean Adults through partnering organizations, social media, such as Kakao Talk which is a popular messaging application among Korean Americans.

The AARIN staff will collaborate with partnering organizations to send a study flyer (**APPENDIX A – HMHL Study Flyer**) to potential participants. AARIN staff will recruit participants directly from partnering organizations by visiting the organization or attending their scheduled activities. AARIN staff will also ask the partnering organizations to refer their potential clients who show interest in participating in the study. Potential participants will share their contact information with partnering organizations for AARIN to contact them with more information about the study.

[name] will call potential participants, speaking in the language of their preference (English or Korean), to describe the study and gauge their interest in participating in the study and their eligibility (**APPENDIX B – Phone Scripts**). Depending on the participant’s capability, enrollment will take place in person, or via zoom/phone. After the eligibility of the participant is confirmed, [name] will present the Consent Information. Though this study will have a waiver of written documentation of consent, [name] will still read through the Consent Information which includes key information about the study. [name] will verify that the participant has heard the Consent Information, was able to ask questions, and has agreed to participate in the study. [name] will administer the screener, present the Consent Information, and administer the Baseline Survey for those eligible and willing to participate. The consent process will be documented in REDCap. (**APPENDIX D – Study Consent & Baseline Variables; APPENDIX E – HMHL Screening & Consent SOP**).

Consent

Since this study is considered “minimal risk” it is exempt from requiring the written documentation of consent. However, the study staff will still present participants with the key information required for informed consent.

In-person Consent Information

[name] will read through a hard copy of the Consent Information with the participant and answer any questions that arise. If the participant has no questions and agrees to participate, [name] will mark an "X" on the Consent Information document to verify the participant has agreed to participate. [name] will track this process and update the participants Consent Information document in REDCap when she uploads the other survey responses. The participant will keep a copy of the Consent Information for themselves.

Online or Phone Consent Information

Prior to the enrollment session, participants enrolling via phone/zoom and who use email will receive an email with the Consent Information in their preferred language, those who do not use email will receive it via mail. If the screener is administered via phone/zoom, participants will provide verbal consent to confirm their participation in the study. The consent document will be read to the participants by [name] once their eligibility has been confirmed through the administration of the screener. If the enrollment is taking place over zoom, the participant will visually see a copy of the Consent Information on the screen through REDCap as the study staff member reads the Consent Information and answers questions. If it is administered via phone, [name] will read the Consent Information to the participant in the participants preferred language. If the participant has no questions, [name] will verbally confirm that the study participant agrees to participate and check's the "agree to participate" in REDCap and mark the document with an "X" to verify the participant has given verbal permission to participate. If a participant indicates they would like to receive the Consent Information via email, REDCap will automatically send the participant a copy of the Consent Information to their designated email address. If they would prefer to receive a paper copy of the Consent Information, the document will be mailed to them at their given address.

The workflow for the recruitment, consent, and data collection for the AARIN staff member and the University of Washington team member are outlined.

Workflow for Development, Recruitment, and Data Collection		
#	Responsibility	Activity
1	University of Washington	Develop the research protocol and consent.
2	University of Washington	Submit the IRB application
3	University of Washington/[name] the MBCT training protocol, the survey instrument and semi-structured interview guide.
4	[name] training on MBCT and provide implementation support.
5	AARIN	Recruit 40 participants for the MBCT program.
6	AARIN	Receive training on MBCT.
7	AARIN	Implement the MBCT program with 40 participants, 5 groups.
8	AARIN	Conduct baseline and post assessment survey – in-person or telephone survey.
9	AARIN	Enter survey data to REDCap.
10	AARIN	Send incentives to participants.
11	AARIN	Conduct and record semi-structured interviews with 12 participants.
12	University of Washington	Transcribe the interviews
13	University of Washington & AARIN	Analyze the data.
14	University of Washington & AARIN	Collaborate on conference presentations and manuscript preparation.

HMHL Intervention

A telephone-based MBCT will be delivered by AARIN staff members. Prior to the delivery of the MBCT the staff members at AARIN will be trained by [name], a certified MBCT instructor and developer of the remote-delivered MBCT protocol. The training will include 1) **experiential training** from participating in the 8-week MBCT intervention, 2) **didactic training** on how to deliver the intervention (how to lead meditations and cognitive exercises

and conduct participants inquiry), and 3) **supervision** as the staff member at AARIN lead their first 8-week MBCT group.

Table 1 shows critical components of MBCT including: (1) learning mindfulness skills; (2) practicing mindfulness skills in class and at home; and (3) dialogue and inquiry. All sessions will be audio-recorded to allow the staff at AARIN to access them later as a resource.

Table 1: Structure and Content of MBCT

Structure	Weekly Content
• Homework review (except session 1)	MBCT-T
• In-session practice of both meditation-based and cognitive behavioral exercises	1. Awareness & Automatic Pilot 2. Living in Our Heads 3. Gathering the Scattered Mind 4. Thoughts are not Facts
• Guided inquiry	5. Allowing and Letting Be (Part I)
• Summary of main themes and assign at-home daily practice	6. Allowing and Letting Be (Part II) 7. Taking Care of Myself 8. Maintenance

[name] will also provide weekly supervision. We will ensure fidelity by using treatment manuals, session fidelity checklists, and weekly supervision of session audio recordings to minimize drift. Treatment fidelity will be evaluated by two independent raters, with a minimum of 85% inter-rater reliability, using the Remote-Delivered MBCT-Treatment Adherence Competence Scale (MBCT-TACS).¹³⁰ We will recruit 40 older Korean Americans. AARIN will deliver five, eight-week MBCT sessions with 8 participants per group (n=40).

Data Collection

Individual participants' mental health status will be assessed at pre and post MBCT delivery using PHQ-9 and quick inventory of Depressive Symptomatology (QIDS) across all conditions (**APPENDIX F – Follow-up survey**). At the end of the study, we will conduct semi-structured interviews with 12-16 older adults to understand acceptability and cultural relevance of the MBCT for older Korean adults (**APPENDIX G – Semi-structured Interview Guide**).

Survey data of participants include depressive symptoms, immigrant stress, sleep quality, socio-demographic characteristics, major chronic diseases, healthcare, beliefs on mental health, and medications. All measures will be collected using validated standardized measures.

Timeline with detailed activities

	2022								2023									
	APR	MAY	JUN	JUL	AUG	SEP	OCT	DEC	JAN	FEB	MAR	APR	MAY	JUN	JUL	AUG	SEP	OCT
Development Research Protocol/Consent/IRB																		
MBCT Training																		
Recruitment																		
Baseline Assessment																		
MBCT Sessions																		
Follow-up Assessment																		
Semi-Structured Interviews																		
Data Analysis																		
Write Summary Report																		
Community Presentation																		

Data Analysis

Survey data Analysis: All analyses will be done in SAS Version 9.4. We will generate frequencies for categorical variables and means for continuous variables. To assess the effect of MBCT, we will compare depression outcomes pre/post using T-test. A two-sided test with a level of 0.05 will be used.

Semi-structured Interview Data Analysis: Transcripts will be uploaded into ATLAS.ti Version 8. Two analysts will use an inductive, constant comparison approach, in which concepts will be identified and themes derived from interview data. Using an iterative process, two analysts will meet weekly to refine the codebook, adding, removing, and revising codes, as needed, to address inter-rater agreement and to compare new data with existing data. We will build consensus around themes that are identified throughout the coding and analysis process. We will compare the themes arising from the data and determine possible linkages across participants and thematic categories.

Data Safety Monitoring Plan

A detailed data safety monitoring plan is outlined in **APPENDIX H.**

REFERENCES:

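### A single-arm pre/post t-test is presented as assessing the effect of MBCT, but it can show only whether mean scores changed

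*Combined protocol and SAP*

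**What the plan says.** Overall Research Design sets out both the design and its purpose: "We will conduct a single arm, pre/post pilot intervention study to examine the effect of MBCT on depression among older Korean American adults". Under Specific Aims, Aim 2 is "To assess the acceptability and relevance of MBCT, as well as its impact on patient reported outcomes among older Korean adults, ages 50-89".

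Data Collection names the outcome scales and times: "mental health status will be assessed at pre and post MBCT delivery using PHQ-9 and quick inventory of Depressive Symptomatology (QIDS) across all conditions". The survey part of Data Analysis then gives the only inferential method for these outcomes: "To assess the effect of MBCT, we will compare depression outcomes pre/post using T-test", two-sided at the 0.05 level. It does not say whether the test is paired.

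PHQ-9 also appears in the Eligibility Criteria, where a score of 5 to 14 is required for entry. Under Participant Recruitment, a staff member "will administer the screener, present the Consent Information, and administer the Baseline Survey for those eligible and willing to participate".

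**The concern.** A pre/post test in one group answers one question: is the mean change different from zero? The effect of MBCT is a different quantity, namely the change with MBCT minus the change the same people would have had without it. The plan has no information on the second term, so no result of this test can estimate the effect.

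The fault therefore lies in the stated inference, not in the data collection. If the plan is followed as written, a significant fall in PHQ-9 or QIDS will be reported as an effect of MBCT even if scores would have fallen anyway. The workflow table foresees conference presentations and a manuscript, and the timeline a summary report and a community presentation, so the wording can carry through to public claims.

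**Working it through.** **What the text supports.** Overall Research Design gives one arm. No section of the supplied text describes a control group, an external comparator, repeated pre-treatment measurements or an adjustment for natural course. Data Collection refers to all conditions, but only one condition is described anywhere. No sentence restricts the conclusion to within-person change. The mismatch between design and claim follows from the text alone and needs no assumption.

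**The plan's own figure.** The HMHL Intervention section gives five groups of 8: 5 × 8 = 40, which reproduces the stated n. There is no power calculation, SD or expected change to reproduce.

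**Illustration of size.** The question is how often the planned test would be significant if MBCT did nothing and scores drifted down by themselves.

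- From the plan: n = 40, two-sided 0.05.
- Assumed, because the plan gives no values: a paired test, an SD of within-person change of 3, 4 or 5 points, and a natural mean fall of 0.5 or 1 point.
- Formula: the paired t statistic follows a noncentral t distribution with 39 degrees of freedom and noncentrality λ = (fall / SD of change) × √40. The test rejects when |t| > 2.023.
- Example: fall 1, SD 3 gives λ = (1/3) × 6.325 = 2.108 and a rejection probability of 53.8%.

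| Natural fall, no MBCT effect | SD of change 3 | SD of change 4 | SD of change 5 |
|---|---|---|---|
| 0 points | 5.0% | 5.0% | 5.0% |
| 0.5 point | λ = 1.054; 17.7% | λ = 0.791; 12.0% | λ = 0.632; 9.5% |
| 1 point | λ = 2.108; 53.8% | λ = 1.581; 33.8% | λ = 1.265; 23.5% |

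As a test of zero change, the t-test behaves correctly in every cell, because the mean really did change. The error arises only when a rejection is read as an effect of MBCT. If pre and post scores are positively correlated, an unpaired test would reject less often, but it would be no more a test of effect.

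**Which PHQ-9 is the pre score?** The text points both ways. Participant Recruitment puts screener, consent and Baseline Survey in one sequence. Against that, the list of appendices separates the screener ("Appendix C – Eligibility Screener") from the Baseline Survey in Appendix D, the workflow table lists recruitment apart from the step "Conduct baseline and post assessment survey – in-person or telephone survey", and the timeline has separate rows for recruitment and baseline assessment. Data Collection also counts depressive symptoms among the survey data. Appendices C and D are not in the supplied text and may settle the matter.

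If the qualifying score is the pre score, selection on 5 to 14 cuts both ends of the scale, with midpoint (5 + 14)/2 = 9.5. In a roughly symmetric screened population with a mean below about 9.5, PHQ-9 would tend to fall on remeasurement without treatment. Near 9.5 there would be little bias, and above it scores would tend to rise. The plan does not give the screened mean, so neither the size nor the direction can be fixed.

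**The case against.** The strongest reply is that this is an openly labelled pilot: the words single arm stand in the same sentence as the word effect, so no reader is misled about the design, and the harm is a forecast about a future report. Part of this stands. A single arm is a legitimate choice for 40 people, the acceptability and relevance parts of Aim 2 are untouched, and the remedy is wording. But the pilot label does not change what the plan says the test is for. A pilot could simply estimate change; this one sets a 0.05 hypothesis test and calls the result the effect of MBCT.

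It can also be objected that the percentages rest on assumed values. That is correct. They show how easily a modest drift reaches significance and are not predictions for this trial.

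A reader might go further and infer that selection on PHQ-9 inflates the result through regression to the mean. The documents do not support this. They do not say that the qualifying score is the pre score, and several passages suggest a separate baseline. If the pre score is a separate measurement with independent error, this bias does not arise and the test keeps about its nominal 5%. Even if the qualifying score is used, the direction depends on an unknown population mean. Any effect on QIDS, which is not the selection scale, would be indirect.

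**Conclusion.** The point holds and should be fixed. The planned t-test cannot assess the effect or impact of MBCT; it assesses mean pre-to-post change. Confidence in this is high, because it rests only on the single arm and the plan's own wording.

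The size is illustrative. Without any MBCT effect, a 1-point natural fall would be called significant in roughly a quarter to a half of such trials, and a 0.5-point fall in roughly one in ten to one in six, given the assumed SDs of change and a paired test.

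Two stronger conclusions should not be drawn: that the single-arm design is itself an error, or that the PHQ-9 change is known to be biased by selection. The second is an open query that unsupplied appendices may answer, not an established fault.

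**What to change.** **Wording of purpose.** In Overall Research Design, state that the study will estimate the pre-to-post change in depressive symptoms among older Korean American adults who take part in MBCT. In Aim 2, replace the reference to impact with the pre-to-post change in patient reported outcomes.

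**Analysis text.** In the survey part of Data Analysis, write:

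> We will report the mean within-person pre-to-post change in PHQ-9 and QIDS with 95% confidence intervals, with a paired t-test of zero change. Because there is no comparison group, the change cannot be separated from natural course and will not be attributed to MBCT.

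**Query to the investigators.** State which PHQ-9 score is the pre score. Only if it is the qualifying score, or one taken in the same contact whose error may be shared with it, add that regression to the mean may bias the PHQ-9 change in either direction, depending on the mean of the screened population. Otherwise no such caveat is needed.

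**Cost.** A few reworded sentences, a confidence interval and one clarification. The arm, the sample size and the planned assessments stay as they are. The downside is a less favourable headline claim.
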